6.3.2 Daily (unless otherwise noted) D6-13

Laboratory Studies:

- **CBC with differential and platelets**
- **Serum Chemistries:** sodium, potassium, chloride, bicarbonate, BUN, serum creatinine, glucose, calcium, magnesium.
- **LDH, Uric acid, phosphate: NOTE,** once tumor lysis syndrome has resolved, these labs do not need to be repeated until D14
- **LFT's:** total protein, albumin, bilirubin (direct and indirect), alkaline phosphatase, AST, ALT: **NOTE: to be drawn every other day**

Concomitant Medications: Review

Toxicity Assessment: via NCI CTCAE V4

6.3.3 Day 14 (Day of Pembrolizumab infusion)

Clinical evaluation: focused history on symptoms/toxicity, physical examination to include weight.

Laboratory studies:

- **Pregnancy Test:** A serum or urine pregnancy test (β -HCG) is required for all women of childbearing potential prior to dose of pembrolizumab. If urine test is positive or cannot be confirmed as negative, a serum pregnancy test will be required.
- **CBC with differential and platelets**
- **Serum Chemistries:** sodium, potassium, chloride, bicarbonate, BUN, serum creatinine, glucose, calcium, magnesium.
- **LFTs: total protein, albumin,** total bilirubin (direct and indirect), alkaline phosphatase, AST (SGOT), ALT (SGPT)
- **Thyroid Function Tests:** TSH, T3, free T4
- **Coagulation Tests:** PT/INR, aPTT, D-Dimer, fibrinogen
- **LDH, Uric acid & phosphate:**

Concomitant Medications: Review (see section 4.4.6)

Toxicity Assessment: via NCI CTCAE v4

Blood sample for Biomarkers: Collect blood sample: see section 6.7 and the laboratory manual for additional details.

6.3.4 Daily (unless otherwise noted) Day 15 until Early Hematologic Recovery or Discharge from Hospital (see footnote #2 for definition)

Laboratory Studies:

- **CBC with differential and platelets**
- **Serum Chemistries:** sodium, potassium, chloride, bicarbonate, BUN, serum creatinine, glucose, calcium, magnesium.
- **LFTs:** total protein, albumin, total bilirubin (direct and indirect), alkaline phosphatase, AST, ALT: **Note: To be drawn every other day**

Blood sample for biomarkers: Collect blood sample weekly between day 14 and hematologic recovery (i.e., day 21, day 28, day 35, day 42 (the latter 2 dates if no hematologic recovery by this time).

- Toxicity Assessment: via NCI CTCAEv4

6.3.5 At Full Hematologic Recovery or on Day 45 +/- 2 days (whichever comes first)

Clinical Evaluation: Physical exam including weight

Laboratory Studies:

- **CBC with differential and platelets**
- **Serum Chemistries:** sodium, potassium, chloride, bicarbonate, BUN, serum creatinine, glucose, calcium, magnesium
- **LFTs:** Total protein, albumin, bilirubin (direct and indirect), alkaline phosphatase, AST, ALT

Toxicity Assessment: via NCI CTCAE v4

Disease Assessment and Biomarkers: Repeat bone marrow biopsy; collect blood sample for biomarkers; see section TBD and laboratory manual for additional details.

6.4 Treatment Assessments-Maintenance

6.4.1 Year 1 of Maintenance

6.4.1.1 Day 1 each Cycle

Clinical evaluation: focused history on symptoms/toxicity, physical examination to include weight, ECOG performance status.

Laboratory studies:

- **CBC with differential and platelets**
- **Serum Chemistries:** sodium, potassium, chloride, bicarbonate, BUN, serum creatinine, glucose, calcium, magnesium
- **LFTs: total protein, albumin,** total bilirubin (direct and indirect), alkaline phosphatase, AST (SGOT), ALT (SGPT)
- **Thyroid Function Tests:** These include TSH, T3, free T4 (D1/C1 and then repeat every 3rd cycle (ie, cycles 3, 6, 9, etc)

Concomitant Medications: Review (see section 4.4.6)

Toxicity Assessment: via NCI CTCAE v4

Blood sample for Biomarkers: Collect blood sample, see section 6.7 and laboratory manual for details

Pembrolizumab administration: 200 mg IV, every 21 days +/- 3 days

Administer QOL Promis SF v1.1 –Global Health questionnaire (optional)

6.4.1.2 After every 4th cycle

Collect bone marrow biopsy for disease assessment and biomarkers: Bone marrow biopsy should be performed after treatment of every 4th cycle at least one day prior to the next treatment cycle; see section 6.7 and laboratory manual for details

6.4.2 Year 2 of Maintenance

6.4.2.1 Day 1 of each cycle

Clinical evaluation: focused history on symptoms/toxicity, physical examination to include weight, ECOG performance status.

Laboratory studies:

- **CBC with differential and platelets**
- **Serum Chemistries:** sodium, potassium, chloride, bicarbonate, BUN, serum creatinine, glucose, calcium, magnesium
- **LFTs: total protein, albumin,** total bilirubin (direct and indirect), alkaline phosphatase, AST (SGOT), ALT (SGPT)
- **Thyroid Function Tests:** These include TSH, T3, free T4 (D1/C1 and then repeat every 3rd cycle (ie, cycles 3, 6, 9, etc)

Concomitant Medications: Review (see section 4.4.6)

Toxicity Assessment: via NCI CTCAE v4

Blood sample for Biomarkers: Collect blood samples every even cycle of treatment (i.e. every other cycle), see section 6.7 and laboratory manual for details

Pembrolizumab administration: 200 mg IV, every 21 days +/- 3 days

Administer QOL Promis SF v1.1 –Global Health questionnaire (optional)

6.4.2.2 After every 6th cycle

Collect bone marrow biopsy for disease assessment and biomarkers: Bone marrow biopsy should be performed after treatment of every 6th cycle (during years 1-2) at least one day prior to the next treatment cycle; see section 6.7 and laboratory manual for details.

6.5 End of Treatment

This visit should occur in patients when they stop treatment whether due to disease progression, unmanageable toxicity, or they have reached 2 years of treatment. In subjects who reach 2 full years of treatment, this visit will take place ~30 days post last dose of pembrolizumab.

Clinical evaluation: Focused history on symptoms/toxicity, physical examination to include weight, ECOG performance status.

Laboratory studies:

- **CBC with differential and platelets**
- **Serum Chemistries:** sodium, potassium, chloride, bicarbonate, BUN, serum creatinine, glucose, calcium, magnesium
- **LFTs: total protein, albumin,** total bilirubin (direct and indirect), alkaline phosphatase, AST (SGOT), ALT (SGPT)

Concomitant Medications: Review (see section 4.4.6)

Toxicity Assessment: via NCI CTCAE v4; patients who experience \geq Grade 2 treatment-related adverse event will be contacted very 2 weeks until the event is

resolved to Grade 0 or 1, determined to be irreversible by the investigator, or until the patient begins an alternate form of drug treatment.

6.6 Follow-up

The first long-term follow-up visit will take place ~ 60 days after the EOT visit (+/- 15 days) and will focus on any serious adverse events (SAEs) or any grade of Events of Clinical Interest that occur within 90 days of the end of pembrolizumab (or prior to start of new anti-cancer therapy). Any such events must be recorded. Subsequent long-term follow up visits will take place as per institutional standard of care (i.e., typically every 3-6 months) and will be limited to history of any subsequent cancer treatments, an assessment of any SAE's considered to be possibly or probably related to study treatment until resolution, and survival status.

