6.0 EVALUATIONS AND ASSESSMENTS

6.1 Time and Events Table

Assessment	Treatment Schedule for Cycle 1 (INDUCTION)									Full Heme Recovery or on D45 +/- 2 days ²	For patients in ≥PR post recovery ³ D1 each cycle; continue cycles for 2 years of MAINTENANCE	EOT ⁴	Follow-up ⁵
	Pre-study ¹	D1 Cycle 1	D2 Cycle 1	D3 Cycle 1	D4 Cycle 1	D5 Cycle 1	D 6-13 Cycle 1	D14 Cycle 1	Daily from D15 until early heme recovery or discharge from hospital ¹³				
Informed Consent	X												
History ⁶	X	X	X	X	X	X		X			X ⁶	X ⁶	X
Physical exam ⁶	X	X						X		X	X	X	X
Performance Status	X	X									X	X	
Pregnancy Test ⁷	X							X					
Echocardiogram	X												
CBC with differential	X	X	X	X	X	X	X	X	X	X	X	X	X
Serum chemistries ⁸	X	BID	BID	BID	BID	BID	X	X	X	X	X	X	X
LDH, Uric acid, phosphate ⁸	X	BID	BID	BID	BID	BID	X ⁸	X					
Liver function tests ⁹	X	X	X	X	X	X	X ⁹	X	X ⁹	X ⁹	X	X	X
Coagulation labs ⁹	X	X	X	X	X	X		X					
Thyroid function tests ¹⁰	X							X			X		
Concomitant meds	X	X	X	X	X	X	X	X	X		X	X	X
Toxicity Assessment		X	X	X	X	X	X	X	X	X	X	X ⁴	X ³
Bone marrow	X ¹¹										X ¹¹	X ¹¹	
Blood sample for biomarkers and buccal cell collection	X ¹²							X ¹²	Weekly ¹²		X ¹²	X ¹²	
Cytarabine IV every 12 hours		X	X	X	X	X							

LCCC 1522
PI: [name]
June 02, 2018

CONFIDENTIAL
UNIVERSITY OF NORTH CAROLINA

Amendment 07

Pembrolizumab 200mg IV								X				X		
Survival analysis														X
QOL Questionnaire ¹⁴												X		

Key to Time and Events Table Footnotes

¹ Unless otherwise noted, evaluations may be performed up to 2 weeks prior to Cycle 1 Day 1 of treatment. Cycle 1 Day 1 laboratory assessments do not need to be repeated if they have been performed up to 72 hours prior to the scheduled visit. **NOTE:** A window of 2 days will be applied to all study visits.

² Full hematologic recovery is defined as absolute neutrophil count $\geq 1,000/\text{mcL}$ and platelet count $\geq 100,000/\text{mcL}$. All assessments listed including a disease assessment via bone marrow biopsy will occur at hematologic recovery, or by day 45 +/- 2 days, whichever comes first. See section 4.2 for additional details regarding D14 pembrolizumab delay.

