³ Patients in $\geq \text{PR}$ based on BM biopsy may continue to receive pembrolizumab every 21 days +/- 3 days (1 cycle) until maintenance treatment duration totals 1 year (see section 4.3 for additional details), disease progression, or intolerable toxicity, whichever occurs first. Pembrolizumab will start 10-60 days post full hematologic recovery in those who achieve PR or CR, and 10-60 days post the post induction bone marrow biopsy in those who achieve CRi. Patients who do not achieve at least a PR, or receive pembrolizumab maintenance by day 60 of hematologic recovery (or day 60 post-induction bone marrow biopsy in CRi patients) will be taken off of protocol-mandated therapy and followed up per protocol.

⁴ This end of treatment (EOT) visit should occur in patients when they stop treatment whether due to disease progression, unmanageable toxicity, or they have reached 2 years of treatment, and will take place ~30 days post last dose of pembrolizumab. Patients who experience $\geq \text{Grade 2}$ treatment-related adverse event will be contacted every 2 weeks until the event is resolved to Grade 0 or 1, determined to be irreversible by the investigator, or until the patient begins an alternate form of drug treatment.

⁵ The first long-term follow-up visits will take place ~60 days after the EOT visit (+/- 15 days) and will focus on any serious adverse events (SAEs) or any grade of Events of Clinical Interest (see section 7.3.4.1) that occur within 90 days of the end of pembrolizumab (or prior to start of new anti-cancer therapy). Any such events must be recorded. Subsequent long-term follow up visits will take place at a schedule as per institutional standard of care (i.e., usually every ~3-6 months) and will be limited to history of any subsequent cancer treatments, an assessment of any SAE's considered to be possibly or probably related to study treatment until resolution, and survival status.

⁶ Complete history at baseline only, thereafter focused history on symptoms/toxicity. Physical exam to include height (baseline only), weight (D1 and D14 of cycle 1, D1 of all cycles of maintenance pembrolizumab and all follow-up visits) and vital signs

⁷ Serum or urine B-HCG within 72 hours prior to D1 of HiDAC and prior to D14 pembrolizumab, and only if clinically appropriate; if the urine test is positive or cannot be confirmed as negative, a serum pregnancy test will be required.

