7.3 SAEs or Serious SARs and Events of Clinical Interest

7.3.1 Timing

After informed consent but prior to initiation of study medications, only SAEs caused by a protocol-mandated intervention will be collected (e.g. SAEs related to invasive procedures such as biopsies, medication washout).

For any other experience or condition that meets the definition of an SAE or a serious SAR, recording of the event must begin from day 1 of study treatment and continue through the 90 day follow-up period after treatment is discontinued (or to the initiation of new anti-cancer treatment, whichever is earliest).

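### The visit that should close the 90-day safety window is timed from the EOT visit, not the last dose, so it may fall before day 90

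*Combined protocol and SAP*

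**What the plan says.** **The visit and its purpose.** Section 6.6 and footnote 5 of the Time and Events Table (Section 6.1) schedule the first long-term follow-up visit in the same way: "The first long-term follow-up visit will take place ~ 60 days after the EOT visit (+/- 15 days"). On its content, footnote 5 says the visit "will focus on any serious adverse events (SAEs) or any grade of Events of Clinical Interest". Its scope is the 90 days after pembrolizumab ends, cut short if new anti-cancer therapy starts. Later visits follow institutional practice, typically every 3 to 6 months. They are limited to subsequent cancer treatment, SAEs possibly or probably related to study treatment, and survival status.

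**The anchor.** Footnote 4 names three reasons for stopping (progression, unmanageable toxicity, 2 years reached) and says for all of them that the EOT visit "will take place ~30 days post last dose of pembrolizumab". Section 6.5 names the same three reasons but splits the timing. In general, "This visit should occur in patients when they stop treatment"; then, separately, "In subjects who reach 2 full years of treatment, this visit will take place ~30 days post last dose of pembrolizumab". It gives no offset for anyone else. Footnote 1 adds: "A window of 2 days will be applied to all study visits".

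**The safety period.** Section 7.3.1 requires SAE recording to "continue through the 90 day follow-up period after treatment is discontinued", or to new anti-cancer treatment if that is earlier. Sections 7.3.4 and 7.3.4.1 require SAEs and ECIs to be reported over the same 90 days whether or not related, shortened to 30 days after cessation if new therapy starts. Non-serious adverse events are documented for only 30 days after treatment (Section 7.2).

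**The concern.** The safety period is counted from the end of pembrolizumab, but the visit meant to review it is counted from another visit. Any variation in when EOT is held carries over to the review, and a symmetric 15-day window is added to that. If the review takes place before day 90, events between the review and day 90 have not yet happened when the patient is asked. The next visit may be months away and is not designed to ask about SAEs judged unrelated or about non-serious ECIs.

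At stake is how complete and comparable late safety data are, chiefly for the secondary objective of characterizing maintenance toxicity (Section 2.2.4). Section 4.3.1 itself warns that immune-related events may appear several months after the last dose. One of the two ECIs listed in Section 7.3.4.1 is a combination of liver-test values, which is found only if blood is drawn. Whether such events come to light would depend partly on how a site schedules EOT and follow-up, and on why the patient stopped.

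**Working it through.** **Inputs.** Follow-up visit at EOT + 60 days, ± 15 (Section 6.6; footnote 5). EOT at about 30 days after the last dose (footnote 4), or unspecified unless the patient completed 2 years (Section 6.5). Safety period of 90 days (Sections 6.6, 7.3.1). I count all days from the last pembrolizumab dose and take the end of treatment to be that dose.

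**Formulas.** Let E be the day of the EOT visit.

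- Visit day = E + 60, range E + 45 to E + 75.
- Days without a scheduled prompt = max(0, 90 − visit day).

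**The plan's own figure.** With E = 30, 30 + 60 = day 90. The nominal schedule reproduces the 90-day period exactly.

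**The range.** The values of E below 30 are my assumptions, because Section 6.5 gives none.

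| EOT day (E) | Earliest | Nominal | Latest | Days short of day 90: nominal (range) |
|---|---|---|---|---|
| 30 (footnote 4) | 75 | 90 | 105 | 0 (0–15) |
| 21 (assumed) | 66 | 81 | 96 | 9 (0–24) |
| 14 (assumed) | 59 | 74 | 89 | 16 (1–31) |
| 7 (assumed) | 52 | 67 | 82 | 23 (8–38) |
| 0 (assumed, extreme) | 45 | 60 | 75 | 30 (15–45) |

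At E = 30, 15 of the 31 permitted days (75 to 105) come before day 90. The largest shortfall is 15/90 = 17% of the period. If EOT also uses the general 2-day window, the range becomes day 73 to 107 and the largest shortfall 17 days. At E = 0 even the latest permitted visit precedes day 90, and the largest shortfall is 45/90 = 50%.

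**Triggers.** Footnote 4 and Section 6.5 list three reasons for an EOT visit. Section 4.6 lists more reasons for ending treatment, including failure to reach PR, CR or CRi after induction, allogeneic transplantation, intercurrent illness and withdrawal. On the planning rates in Section 8.1 (CR/CRi 20% to 40%; PR 0 to 5%, a range stated there under the null), non-response would be between 100 − 40 − 5 = 55% and 100 − 20 − 0 = 80%. The unlisted exits are therefore not a small group.

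**The case against.** The strongest reply is that the schedule is centred correctly. Footnote 4 covers every reason it lists, the nominal visit is on day 90, and a shortfall arises only if a site uses the early half of the window. That stands, and it limits the footnote 4 case to 15 days (17 with the EOT window).

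Second, capture does not depend on this visit alone. Sections 7.3.1, 7.3.4 and 7.3.4.1 oblige sites to record or report through day 90, SAEs related to pembrolizumab are reportable at any time, and patients with a grade 2 or higher treatment-related event are contacted every 2 weeks (footnote 4; Section 6.5). That also stands. It would be wrong to infer that the last weeks go unmonitored: what lacks a scheduled prompt is unrelated SAEs and non-serious ECIs. The duty is not a full substitute, because a site can report only what it learns.

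Third, a reader might infer from Section 6.5 that half the period is routinely lost. The documents do not support this. It needs EOT on the day of the last dose and the earliest permitted visit together. Non-response, for example, is established at the marrow on recovery or about day 45. For a day-14 dose and a day-45 marrow that is 45 − 14 = 31 days after dosing, close to the footnote 4 offset. An earlier recovery marrow would shorten this.

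Fourth, a reader might say that every treated patient is affected. The period closes when new anti-cancer therapy starts, so many who stop for progression or non-response may have no gap.

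Fifth, the median onsets of 1.5 to 6.5 months in Section 5.1.6 might be read as showing that days 75 to 90 are a high-risk time. They describe treated melanoma patients and are not stated as times since the last dose. Section 4.3.1 supports the relevance of late events but gives no rate.

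Finally, one might say that non-responders have no EOT date at all. Both texts trigger EOT when treatment stops, and footnote 3 has these patients followed per protocol. The fair reading is an incomplete list of reasons, not a missing visit.

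**Conclusion.** The point holds as a modest weakness in late-safety ascertainment. The only scheduled contact meant to review all SAEs and any-grade ECIs over 90 days may be held up to 15 days early under footnote 4, and earlier under the Section 6.5 wording, where 45 days is the extreme and not the expected case. The shortfall applies to unrelated SAEs and non-serious ECIs, in patients who have not started new anti-cancer therapy.

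The effect is possible under-ascertainment. A definite downward bias in the maintenance toxicity estimate is a tempting further step, but it is not shown. The documents give no event rate for these days and no distribution of visit dates, drug-related SAEs remain reportable, and patients who stop after induction do not enter the maintenance estimate. The primary endpoint and sample size are unaffected.

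The 15-day figure rests on the documents alone. The larger figures rest on assumed EOT dates that Section 6.5 does not exclude.

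**What to change.** In Section 6.6 and footnote 5, time the existing first follow-up visit or call from the last pembrolizumab dose, not before day 90 (for example day 90 with a window of 0 to +15 days). State that this applies whatever the reason for stopping, including non-response after induction. At day 90 to 105 the part of the period without a scheduled prompt becomes 0 days.

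Reconcile the EOT timing in footnote 4 and Section 6.5, and bring the reasons listed in both into line with Section 4.6. Changing the follow-up anchor alone would leave that discrepancy in place.

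The cost is a few wording changes and no additional visits. Some visits would move later: by up to 15 days if EOT is at day 30, and by up to a few weeks where EOT is now held earlier.

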6.7 Correlative Studies Procedures

These are described in more detail in the laboratory manual. NOTE: A tumor sample will be sent to Merck or their designated laboratory for evaluation of PD-L1 expression at baseline. See laboratory manual for additional details.

Samples will be processed within 24 hours of collection as outlined in the Standard Operating Procedure Guidelines in the Laboratory Manual.

Some of the specific correlative details regarding specific antibodies, repertoires etc. may vary from this protocol, but will be maintained and updated in the corresponding laboratory manual.

6.7.1 mRNA Sequencing (mRNA-seq) and Proteomics

mRNA-seq of bulk bone marrow leukocyte samples from diagnostic specimens will be performed for definition of tumor genetic subtypes, quantification of PD-L1 mRNA expression, and evaluation of gene expression signatures associated with immune activation and suppression. Bulk bone marrow leukocyte samples will also be sorted into CD34⁺ and CD34⁻ subpopulations, and the CD34⁺ populations will undergo 1) mRNA-seq for neoantigen prediction and analysis of differential splicing, and 2) mass spectrometry for neoantigen confirmation. The CD34⁻ fraction will be stored for the generation of cytotoxic T lymphocyte cultures for confirmation of biologically valid neoantigens.

The mRNA-seq studies will involve genetic research where tumor gene expression profiling and analysis of somatic mutations will be included. Appropriate informed consent for genetic research will be obtained prior to patient samples being processed.

6.7.2 High-Throughput DNA sequencing

Whole exome sequencing of CD34⁺ AML blasts from bone marrow samples will be performed for somatic mutation detection and neoantigen prediction. From

bone marrow and peripheral blood leukocyte samples, T cell functional studies will be performed, and T cell receptor (TCR) and B cell receptor (BCR) repertoires will be amplified, sequenced, and analyzed to discover receptor profiles that correlate with response to therapy.

6.7.3 Flow Cytometry/Immunohistochemistry of Immune Markers

Bone marrow core biopsy blocks/slides may be stained for coexpression using the following panel of fluorescent antibodies (can include but not limited to): CD4/FoxP3, CD8/PD1, CD19/CD27, CD11b/CD33, CD47/CD68, along with immunohistochemistry staining using the following antibodies: PD-L1, IFN- γ , TNF- α , CTLA4, KIR3DL1, LAG3, CD200, Tim3 (HAVCR2), BTLA, CD137 (TNFRSF9), CD40, OX40, CD27, ICOS, and GTR (TNFRSF18), which combined will enable quantification and localization of effector T cells, regulatory T cells, myeloid derived suppressor cells, antigen-experienced vs. non-experienced B cells, and suppressive macrophages.

